**Table 4. Summary of Lab DLTs.**

**Non-Lab Toxicity**

AE	Patient Population	Dose Limiting Toxicity
Rash (acneiform or macro-papular)	All	≥ Grade 3
Palmar-plantar erythrodysethesia syndrome	All	Grade 3
Hypertension	Uncontrollable to less than 150/90 with maximal medical management within 7 days	≥ Grade 3
Bronchopulmonary hemorrhage (hemoptysis)	All	≥ Grade 3
Mucositis oral (Stomatitis)	Non-responsive to maximal supportive medication within 7 days	≥ Grade 3
Other Non-Lab Toxicity	All	≥ Grade 3 with the EXCEPTION of the following: 
 
• nausea, vomiting, diarrhea, constipation or edema controllable with medication within 7 days
 
• grade 3 fever in the absence of infection or neutropenia
 
• tumor flare defined as local pain, irritation or rash localized at sites of known or suspected tumor
 
• transient grade 3 infusion reaction
 
• grade 3 thromboembolic event IF patient is asymptomatic and initiated on anticoagulation – as there is a high prevalence in sarcomas, and this is difficult to attribute to study drug.
 

**Table 5. Summary of Non-Lab DLTs.**

### 8.0 TREATMENT PLAN

A cycle of treatment will consist of concurrent axitinib and pembrolizumab therapy for 6 weeks (Figure 3, Table 6), except for cycle 1 which will be 7 weeks as detailed above. Administration of axitinib shall occur continuously with pembrolizumab administered on day 8 and day 29 of the first cycle, and days 1 and 22 of the following cycles. The first five patients will not be dose-escalated above 5 mg PO twice daily axitinib. If these patients exhibit acceptable rates of DLT, starting with patient 6, dose-escalation of axitinib will be permitted. No dose escalations will be permitted during cycle 1. On day 1 of cycle 2 and the subsequent cycles, dose escalation of axitinib is permitted if toxicity is within the specified criteria. No dose-escalation will be conducted in the middle of any cycle. Dose reduction or interruption is permitted in the case of toxicity at any time as per section 10.0.

Trial treatment should be administered after all procedures/assessments have been completed as detailed in Section 12.0. Trial treatment may be administered up to 3 days before or after the scheduled Day 1 of each cycle due to administrative (e.g. scheduling) reasons.

Cycle(s)	1							2						Imaging prior to every subsequent odd cycle (i.e. 3, 5, 7, 9, etc.)	3, 4, 5, etc. until progression					
	1	2	3	4	5	6	7	1	2	3	4	5	6		1	2	3	4	5	6
Week(s)	1	8	1	2	2	3	4	1	8	1	2	2	36	1	8	1	2	2	3	
Day(s)	1	8	5	2	9	6	3	1	8	5	2	9	36	1	8	5	2	9	6	
Axitinib oral, BID continuously (uptitration permitted starting from cycle 2)	X	X	X	X	X	X	X	X	X	X	X	X	X	X	X	X	X	X	X	
Pembrolizumab IV q21 days		X			X			X			X			X			X			

**Table 6. Treatment Schema: Axitinib and Pembrolizumab Concurrent Therapy**

Once patients have completed two years of combination treatment with axitinib/pembrolizumab, pembrolizumab treatment will be stopped and patients will be treated with axitinib alone until progression. Each treatment cycle is 84 days (12 weeks) in length. Imaging will be performed every 12 weeks ( $\pm 7$  days).

Cycle(s)	1, 2, 3, etc. until progression												Imaging every 12 weeks (+/- 7 days)
Week(s)	1	2	3	4	5	6	7	8	9	10	11	12	
Day(s)	1	8	15	22	29	36	43	50	57	64	71	78	
Axitinib oral, BID continuously	X	X	X	X	X	X	X	X	X	X	X	X	

**Table 7. Treatment Schema: Axitinib Monotherapy**

For patients who progress while on axitinib monotherapy, pembrolizumab can be re-introduced and patients can be treated with the axitinib/pembrolizumab combination treatment for up to 17 additional cycles (approximately 1 year). A cycle of treatment will consist of axitinib/pembrolizumab combination therapy for 6 weeks (Table 8). Administration of axitinib shall occur continuously with pembrolizumab administered on days 1 and 22.

Once participants complete the additional year of axitinib/pembrolizumab treatment, they will continue with axitinib monotherapy indefinitely until they experience toxicity, withdrawal or consent, or as per the treating physician’s discretion. The indefinite axitinib monotherapy treatment schema will be the same as for the axitinib monotherapy (Table 7).

Cycle(s)	1, 2, 3, etc. up to 17 cycles (approximately 1 year)						Imaging prior to every subsequent odd cycle (i.e. 3, 5, 7, 9, etc.)
Week(s)	1	2	3	4	5	6	
Day(s)	1	8	15	22	29	36	
Axitinib oral, BID continuously	X	X	X	X	X	X	
Pembrolizumab IV q21 days	X			X			

**Table 8. Treatment Schema: Axitinib/Pembrolizumab Combination Treatment for Patients who Progress while on Axitinib Monotherapy**

				First 2 years of combination Axitinib/Pembrolizumab treatment		Axitinib Monotherapy (until progression) ***		Combination Axitinib/Pembrolizumab treatment (Additional Year)	
Agent	Premedications & Precautions	Dose	Route	Schedule	Cycle Length* *	Schedule	Cycle Length	Schedule	Cycle Length
Axitinib	Premedicate with ondansetron 8 mg orally if needed for nausea  Take daily doses 12 hours apart and swallow whole with or without food with a glass of water	* 5mg	PO BID	** Days 1-42 (week 1-6)	42 days (6 weeks) **	Days 1-84 (week 1-12)	84 days (12 weeks)	** Days 1-42 (week 1-6)	42 days (6 weeks) **
Pembrolizumab	Monitor for infusion reactions with hypersensitivity kit at bedside.  Grade 2 infusion reactions will be premedicated with diphenhydramine 50 mg IV and acetaminophen 1000 mg PO prior to subsequent infusions.  Diet: Subjects should maintain a normal diet unless modifications are required to manage an AE such as diarrhea, nausea or vomiting.	200 mg	IV infusion over 30 minutes (-5min/+10min)	Cycle 1: Day 8, 29  Subsequent cycles: Day 1, 22		NA	NA	Each Cycle: Day 1, 22	
*Inpatient dose escalation permitted after 5-patient safety lead-in as per protocol. ** Cycle 1 is 7 weeks with the first week consisting of axitinib alone. *** Axitinib indefinite treatment will follow the same schedule as axitinib monotherapy									

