Cycle(s)	1							2						3, 4, 5, etc. until progression																																																																																																																																			
	1		2	3	4	5	6	7	1	2	3	4	5		6		1	2	3	4	5	6																																																																																																																											
	1	8	15	22	29	36	43	1	8	15	22	29	36		1	8	15	22	29	36																																																																																																																													
Axitinib oral, BID continuously (up-titration permitted beginning in cycle 2)	X	X	X	X	X	X	X	X	X	X	X	X	X																																																																																																																																				
Pembrolizumab IV q21 days		X			X			X			X			X			X																																																																																																																																
Cycle(s)	1, 2, 3, etc. until progression												Imaging every 12 weeks (+/- 7 days)																																																																																																																																				
	1	2	3	4	5	6	7	8	9	10	11	12																																																																																																																																					
	1	8	15	22	29	36	43	50	57	64	71	78																																																																																																																																					
Axitinib oral, BID continuously	X	X	X	X	X	X	X	X	X	X	X	X																																																																																																																																					

Treatment Schema: Axitinib/Pembrolizumab Combination Treatment for Patients who Progress while on Axitinib Monotherapy	
Cycle(s)	1, 2, 3, etc. up to 17 cycles (approximately 1 year)
Week(s)	1      2      3      4      5      6
Day(s)	1      8      15      22      29      36
Axitinib oral, BID continuously	X      X      X      X      X      X
Pembrolizumab IV q21 days	X   X  
	Imaging prior to every subsequent odd cycle (i.e. 3, 5, 7, 9, etc.)
Duration of Treatment	Trial therapy will last until withdrawal of consent, disease progression and/or unacceptable toxicity, whichever occurs first.

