**Table 9. Axitinib and Pembrolizumab Regimen Description**

### 8.1 **Second Course Axitinib (Inlyta®)**

All participants who complete the first two years of axitinib/pembrolizumab combination treatment may be eligible for axitinib monotherapy treatment until progression.

For participants who progress while on the axitinib monotherapy treatment, pembrolizumab can be re-introduced and participants will be treated with the axitinib/pembrolizumab combination treatment for up to 17 additional cycles (approximately 1 year). Once participants complete the additional year of axitinib/pembrolizumab treatment, they will continue with axitinib monotherapy indefinitely until they experience toxicity, withdrawal or consent, or as per the treating physician's discretion.

This retreatment is termed the Second Course Phase of this study and is only available if the study remains open and the participant is receiving clinical benefit from treatment.

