### 8.2 **Second Course Pembrolizumab**

All participants who complete the first two years of axitinib/pembrolizumab combination treatment may be eligible for pembrolizumab retreatment if they progress while on axitinib monotherapy treatment. Pembrolizumab will be given as an axitinib/pembrolizumab combination treatment for up to 17 additional cycles (approximately 1 year).

Pembrolizumab re-introduction will be given for participants who progress while on axitinib monotherapy. This retreatment is termed the Second Course Phase of this study and is only available if the study remains open and the participant is receiving clinical benefit from treatment.

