### 8.4 **Pembrolizumab (Keytruda®)**

Pembrolizumab 200 mg flat dose shall be administered in the outpatient setting as a 30 minute intravenous (IV) infusion, once every 21 days. The intravenous line should contain a sterile, non-pyrogenic, low-protein binding 0.2 micron to 5 micron in-line or

add-on filter. Do not co-administer other drugs through the same infusion line. Every effort to target infusion timing to be as close to 30 minutes as possible, should be made. However, given the variability of infusion pumps from site to site, a window of -5 minutes and +10 minutes is permitted (i.e. infusion time is 30 minutes: -5 min/+10min).

For additional information on pembrolizumab including mechanism of action, drug metabolism, pharmacokinetics & toxicology, known side effects, composition, and storage recommendations, see [Section 9.2].

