## 8.5 Treatment Dispensation, Compliance and Accountability

Concurrent administration of axitinib/pembrolizumab therapy will continue for each cycle until criteria for treatment discontinuation is/are met (See section 11.0). Once patients have completed two years of combination treatment with axitinib/pembrolizumab, pembrolizumab treatment will be stopped and patients will be treated with axitinib alone. For patients who progress while being on treatment with axitinib monotherapy, pembrolizumab can be re-introduced with the axitinib treatment, and patients can be treated with the axitinib/pembrolizumab treatment for up to an additional 17 cycles (approximately 1 year).

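### The second-course cap of 17 six-week cycles is 102 weeks and 34 infusions, about twice the one year written beside it

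*Combined protocol and SAP*

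**What the plan says.** Section 8.0 describes three phases: two years of axitinib plus pembrolizumab, then axitinib alone until progression, then, for those who progress, the combination again. The last phase is allowed "for up to 17 additional cycles (approximately 1 year"). The sentence after it fixes the unit: "A cycle of treatment will consist of axitinib/pembrolizumab combination therapy for 6 weeks (Table 8"), with pembrolizumab on days 1 and 22.

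The rest of the protocol repeats both halves of this:

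- **Cap with its one-year gloss.** The Synopsis treatment schema has "1, 2, 3, etc. up to 17 cycles (approximately 1 year"), and Table 8 carries the same label. Section 8.1 repeats the pairing. Section 8.2 says "Pembrolizumab will be given as an axitinib/pembrolizumab combination treatment for up to 17 additional cycles (approximately 1 year"), and Section 8.5 says "for up to an additional 17 cycles (approximately 1 year").
- **Six-week cycle with two infusions.** Table 8 draws six weeks with infusions in weeks 1 and 4. Table 9 gives 42 days and infusions on days 1 and 22 of each cycle, under the heading "Combination Axitinib/Pembrolizumab treatment (Additional Year"). Sections 12.2.19 and 12.2.20 schedule day 1 and day 22 visits for all re-introduction cycles.
- **Dosing interval.** Section 8.4 gives 200 mg as a "30 minute intravenous (IV) infusion, once every 21 days".
- **Exit from the phase.** Sections 8.0, 8.1 and 8.5.1 move patients to indefinite axitinib monotherapy "Once participants complete the additional year of axitinib/pembrolizumab treatment".

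**The concern.** The cap is stated as a number of cycles and as a length of time, and the two cannot both be right when a cycle lasts six weeks. The Synopsis and the body agree with each other, so neither corrects the other. The error is in the plain prose of several sections as well as in the tables.

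What is at stake is a ceiling on investigational dosing and the date on which a patient leaves combination treatment. Staff who count the protocol's numbered cycles to 17 and staff who stop after a year could both claim compliance, and their patients would differ twofold in maximum second-course pembrolizumab. Second-course exposure and safety summaries would then mix the two practices.

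**Working it through.** **Inputs**

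- Cap: 17 cycles, glossed as about 1 year (Synopsis schema; Sections 8.0, 8.1, 8.2, 8.5; Table 8).
- Cycle length: 6 weeks, or 42 days (Section 8.0, Tables 8 and 9).
- Infusions per cycle: 2, on days 1 and 22 (Section 8.0, Tables 8 and 9, Sections 12.2.19 and 12.2.20).
- Dose and interval: 200 mg every 21 days (Section 8.4).

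**Can the stated year be reproduced?** Duration = number of cycles x cycle length.

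| Cycle length tried | Source | 17 cycles | Years |
|---|---|---|---|
| 6 weeks | the cycle defined for this phase | 102 weeks = 714 days | 714/365.25 = 1.95 |
| 12 weeks | the axitinib monotherapy cycle (Table 7) | 204 weeks = 1,428 days | 1,428/365.25 = 3.91 |
| 3 weeks | one pembrolizumab interval | 51 weeks = 357 days | 357/365.25 = 0.98 |

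Only three weeks reproduces the year, and the protocol nowhere defines a three-week cycle for this phase. Table 9 also attaches to the additional-year axitinib entries the footnote under which cycle 1 lasts seven weeks. Applying it gives 103 weeks and still 34 infusions.

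**Exposure if cycles are counted**

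- Infusions: 17 x 2 = 34.
- Last infusion: day 1 + 33 x 21 = day 694, which is day 22 of cycle 17.
- Total dose: 34 x 200 = 6,800 mg.

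**Exposure if a year is counted**

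- Six-week cycles in a year: 365.25/42 = 8.7.
- Infusions every 21 days in a year: 365.25/21 = 17.4, so 17 complete intervals, covering 51 weeks.
- 17th infusion: day 1 + 16 x 21 = day 337. Since 8 x 42 = 336, this is day 1 of cycle 9.
- Total dose: 17 x 200 = 3,400 mg.

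**Ratio:** 6,800/3,400 = 2.0.

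**Likely source of the 17.** Section 11.0 pairs 24 months of pembrolizumab with 35 administrations, and 35 x 21 = 735 days = 2.01 years. So the protocol elsewhere counts pembrolizumab by three-weekly administrations, and 17 fits one year on that count. This explains the error plausibly, but no text states it.

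**The case against.** Nobody need dispute the arithmetic. The case against concerns how much it matters.

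1. **Duration already works as the stopping event.** The sentences that move a patient to indefinite axitinib refer to completing the additional year, while 17 is only a maximum and always carries the one-year gloss. Staff who follow those sentences stop at about a year. This makes the double-length reading less likely and supports one year as the intent. It does not settle the matter: the stated maximum contradicts those sentences in five sections, and no rule gives either precedence.
2. **The harm is quoted at its ceiling.** Dose per infusion and interval do not change. Thirty-four infusions is no longer than the first course allowed by Section 11.0. Day 1 and day 22 visits continue, and discontinuation for toxicity or on the investigator's judgement still applies. All of this is fair. The 6,800 mg and day 694 figures describe a patient treated without interruption to the cap, and they would come on top of a completed first course.
3. **The reach is narrow.** A patient must complete two years of combination, progress on monotherapy, be re-treated while the study is open and treatment is of benefit, and still be on the combination after a year. This stands. The documents do not show how many patients that would be.
4. **A cap of 17 infusions ends on day 1 of a six-week cycle.** This is a drafting detail and can be settled in the same edit.

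**Conclusion.** The concern holds. As written, the second-course cap is 102 weeks and 34 infusions, 1.95 times the year beside it, with twice the pembrolizumab of a 17-infusion course. This rests only on the protocol's own cycle length and infusion days, and no other defined cycle length reconciles the two figures. That one year was intended is well supported by the additional-year wording. That 17 was meant as a count of infusions is an inference.

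It must be fixed because a dosing limit needs one executable meaning and this one has two that differ by a factor of two. The consequence is confined to second-course exposure and safety. The 3-month PFS endpoint, ORR and the sample size are unaffected.

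**What to change.** In the Synopsis schema, the Section 8.0 text, Table 8, and Sections 8.1, 8.2 and 8.5, restate the cap as up to 17 pembrolizumab infusions, one every 21 days (about 8 to 9 six-week cycles, approximately 1 year). Make the infusion count the governing limit, because 8 to 9 cycles alone spans 16 to 18 infusions.

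In the same edit:

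- Say what follows the 17th infusion on day 1 of cycle 9. For example, the patient could complete that 21-day interval and then start the 84-day axitinib schedule.
- Remove the seven-week cycle 1 footnote from the additional-year entries of Table 9.

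If 17 six-week cycles are really intended, change the duration in those same places to approximately 2 years (34 infusions). Then correct the additional-year wording in Sections 8.0, 8.1 and 8.5.1 and in the Table 9 heading.

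Either version costs protocol wording only. Design, endpoints, sample size and analysis do not change.

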**Table 9. Axitinib and Pembrolizumab Regimen Description**

### 8.1 **Second Course Axitinib (Inlyta®)**

All participants who complete the first two years of axitinib/pembrolizumab combination treatment may be eligible for axitinib monotherapy treatment until progression.

For participants who progress while on the axitinib monotherapy treatment, pembrolizumab can be re-introduced and participants will be treated with the axitinib/pembrolizumab combination treatment for up to 17 additional cycles (approximately 1 year). Once participants complete the additional year of axitinib/pembrolizumab treatment, they will continue with axitinib monotherapy indefinitely until they experience toxicity, withdrawal or consent, or as per the treating physician's discretion.

This retreatment is termed the Second Course Phase of this study and is only available if the study remains open and the participant is receiving clinical benefit from treatment.

### 8.2 **Second Course Pembrolizumab**

All participants who complete the first two years of axitinib/pembrolizumab combination treatment may be eligible for pembrolizumab retreatment if they progress while on axitinib monotherapy treatment. Pembrolizumab will be given as an axitinib/pembrolizumab combination treatment for up to 17 additional cycles (approximately 1 year).

Pembrolizumab re-introduction will be given for participants who progress while on axitinib monotherapy. This retreatment is termed the Second Course Phase of this study and is only available if the study remains open and the participant is receiving clinical benefit from treatment.

### 8.3 **Axitinib (Inlyta®)**

Axitinib shall be administered in the outpatient setting as either 5mg or multiple 1 mg tablets, orally (PO) twice a day (BID) continuously, with dose titration as per section 10.0.

Patients are to be advised that daily doses of axitinib shall be taken 12 hours apart with or without food and swallowed whole with a glass of water.

For additional information on Axitinib including mechanism of action, drug metabolism, pharmacokinetics & toxicology, known side effects, composition, and storage recommendations, see [Section 9.1].

### 8.4 **Pembrolizumab (Keytruda®)**

Pembrolizumab 200 mg flat dose shall be administered in the outpatient setting as a 30 minute intravenous (IV) infusion, once every 21 days. The intravenous line should contain a sterile, non-pyrogenic, low-protein binding 0.2 micron to 5 micron in-line or

add-on filter. Do not co-administer other drugs through the same infusion line. Every effort to target infusion timing to be as close to 30 minutes as possible, should be made. However, given the variability of infusion pumps from site to site, a window of -5 minutes and +10 minutes is permitted (i.e. infusion time is 30 minutes: -5 min/+10min).

For additional information on pembrolizumab including mechanism of action, drug metabolism, pharmacokinetics & toxicology, known side effects, composition, and storage recommendations, see [Section 9.2].

## 8.5 Treatment Dispensation, Compliance and Accountability

Concurrent administration of axitinib/pembrolizumab therapy will continue for each cycle until criteria for treatment discontinuation is/are met (See section 11.0). Once patients have completed two years of combination treatment with axitinib/pembrolizumab, pembrolizumab treatment will be stopped and patients will be treated with axitinib alone. For patients who progress while being on treatment with axitinib monotherapy, pembrolizumab can be re-introduced with the axitinib treatment, and patients can be treated with the axitinib/pembrolizumab treatment for up to an additional 17 cycles (approximately 1 year).

### 8.5.1 Axitinib

During the first two years of axitinib/pembrolizumab combination treatment, eligible patients will be dispensed the appropriate number of axitinib tablets required for at least 21 days of dosing plus an additional 3-day supply to account for visit scheduling.

Once participants have completed the first two years of axitinib/pembrolizumab combination treatment, eligible patients will be treated with axitinib monotherapy until progression. During this time, eligible patients will be dispensed the appropriate number of axitinib tablets required for at least 84 days of dosing plus an additional 3-day supply to account for visit scheduling.

Pembrolizumab will be re-introduced for participants who progress while being treated with axitinib monotherapy. Eligible patients will be dispensed the appropriate number of axitinib tablets required for at least 21 days of dosing plus an additional 3-day supply to account for visit scheduling.

Once participants complete the additional year of axitinib/pembrolizumab treatment, they will continue with axitinib monotherapy indefinitely until they experience toxicity, withdrawal or consent, or as per the treating physician's discretion. During this time, eligible patients will be dispensed the appropriate number of axitinib tablets required for at least 84 days of dosing plus an additional 3-day supply to account for visit scheduling.

Treatment compliance will be assessed based on return of unused axitinib tablets and a dosing diary. Eligible patients will be given a dosing diary for each treatment cycle. Date, time, and dose should be recorded at each dosing time point to confirm that each BID dose of axitinib was taken for each day.

The medication diary will be reviewed weekly during each week of axitinib administration (at a minimum during the first 3 weeks of each cycle, or otherwise noted) and returned to clinic staff at the end of each cycle. See Appendix I for the dosing diary. During the first cycle of axitinib, or for the first three weeks after any dose escalation or reduction of axitinib, patients will also be asked to record their blood pressure at least once each day before their evening dose of axitinib. See also Appendix I for the blood pressure diary.

If a dose of axitinib is missed due to patient error/oversight, then he/she should take the axitinib dose within 2 hours of the missed dose. If more than 2 hours have elapsed, that missed dose should be omitted, the patient should resume treatment at the next scheduled dosing time point, and the reason for missed dose reported on the dosing diary. If the patient vomits, an additional dose should not be taken. The next prescribed dose should be taken at the usual time.

If a dose of axitinib is held due to AE, SAE, or at the investigator's discretion, then he/she should resume treatment at the investigators discretion taking into account all of the dose modification/discontinuation guidelines provided in Section 10.0 Treatment/Dose Modifications.

